12.2.2 Psychosocial & Privacy Risks

Any time information is collected there is a potential for loss of confidentiality. Every effort will be made to keep participant's information confidential, however this cannot be guaranteed. Participation in research study may make participants feel uncomfortable. Participants will be informed that they may refuse to participate or stop their participation at any time without effect on future medical treatment or relationship with the treating physician.

12.2.3 Adverse Event Reporting

An Adverse Event (AE) is any untoward sign, symptom or medical condition occurring at any time after the subject receives his/her procedure, even if the event is not considered to be related to the study. Abnormal laboratory values or test results constitute AEs only if they induce clinical signs or symptoms, are considered clinically significant, or require therapy.

The adverse events that will be monitored and reported from the start of the study procedure until 1 year after the index procedure are complications related to the procedure which include:

- Bleeding
- Hematoma
- Radial Occlusion

A Serious Adverse Event (SAE) is an undesirable sign, symptom or medical condition which:

- is fatal
- is life threatening
- requires or prolongs hospitalization
- results in persistent or significant disability/incapacity
- constitutes a congenital anomaly or a birth defect
- is medically significant, in that it may jeopardize the subject and may require medical or surgical intervention to prevent 1 of the outcomes listed above
- Hospitalizations not necessarily considered to be SAEs are hospitalizations for:
- treatment, which was elective or preplanned, for a pre-existing condition that is unrelated to the indication under study and did not worsen
- treatment on an emergency, outpatient basis for an event not fulfilling any of the definitions of serious given above and not resulting in hospital admission

All SAEs will be followed up until resolution or permanent outcome of the event.

13. RISK/BENFIT ASSESSMENT

Local hematoma formation or prolonged compression may cause sensory damage or ischemia after radial access interventions. Distal radial access allows the arm to stay in a more natural and comfortable position for the patient and may reduce the risk of bleeding and artery occlusion. Advancing the understanding of distal radial access procedures will contribute to potentially easier and safer peri-procedural management of patients undergoing cardiac catheterization.

14. STATISTICAL METHODS

14. Statistical Methods

Patient demographics and characteristics will be reported and compared between the radial distal access (rDA) and proximal distal access (pDA) cohorts. Continuous variables will be reported as means ± standard deviations or medians [quartile 1, quartile 3], if skewed. Categorical variables will be reported as frequencies and percentages. Differences between demographic and clinical variables, as well as safety and compliance, will be assessed via two sample t-tests and Chi-square tests (or Wilcoxon's Rank Sum test and Fisher's Exact test), as appropriate.

14.1 Analysis of Primary Composite Outcome

The primary composite outcome of hand function will be defined utilizing the average Z-score approach (O'Brien, 1984; Sun, 2012). The average z-score for each subject is calculated as the average of the z-scores of the differences between pre- and 1-month post-operation measurements for three individual tests. The three tests that measure everyday functionality and strength of a subject's hand included in the composite outcome are: (a) the QuickDASH questionnaire score (0-100) calculated as [(sum of n responses / n) – 1] * 25, (b) Thumb and forefinger pinch strength test (kg), and (c) hand grip strength test (kg). The average of the three z-scores are then compared between rDA and pDA using the Wilcoxon rank-sum test.

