		12.2.1 Physical Risks	
		12.2.2 Psychosocial and Privacy Risks	
4.0	BIOK	12.2.3 Adverse Event Reporting	
13	-		
14			
15		CEDURES AND INSTRUCTIONS	
	15.1	PROTOCOL AMENDMENTS	
	15.2	RECORDING OF DATA, DOCUMENTATION, AND RETENTION OF DOCUMENTS	
	15.3	PUBLICATION OF RESULTS	
	15.4	DISCLOSURE AND CONFIDENTIALITY	
16		CS AND GOOD CLINICAL PRACTICE	
	16.1	INSTITUTIONAL REVIEW BOARD/INDEPENDENT ETHICS COMMITTEE	
47	16.2	INFORMED CONSENT	
17	REFE	RENCES	16

Abbreviation	Term
AE	Adverse event
CABG	Coronary artery bypass grafting
CBC	Complete blood count
DASH	Disabilities of the Arm, Shoulder, and Hand Questionnaire
dRA	Distal radial artery
e-CRF	Electronic case report form
HIPAA	Health Insurance Portability and Accountability Act of 1996
ICH	International Council for Harmonisation
IRB	Institutional Review Board
PCI	Percutaneous coronary intervention
PHI	Protected health information
PI	Principal Investigator
pRA	Proximal radial artery
SAE	Serious adverse event

ABBREVIATIONS

SYNOPSIS	
Summary/Rationale:	This single-center, prospective, randomized study will evaluate distal radial artery (dRA) vs. proximal radial artery access (pRA) in regards to hand function and radial artery occlusion.
Study Objectives:	 Primary objective is to evaluate hand function following distal radial artery access compared to proximal artery access in patients undergoing cardiac catheterization. Hand function will be assessed by: QuickDASH questionnaire Hand grip test Thumb forefinger pinch test utilizing a pinch gauge Secondary objectives: Vascular access success rates, hematoma, bleeding, complications of vascular access and radial artery occlusion.
Study Design:	Single-center, prospective, randomized, study
Study Intervention(s):	Distal and proximal radial artery access
Number of Subjects:	300
Inclusion Criteria:	 A patient will be eligible for inclusion in this study if he or she meets all of the following criteria: 1. Age ≥ 18 years. 2. The distal and proximal radial artery must be palpable and non-occlusive flow must be confirmed by (Doppler) ultrasound. 3. Patient should be able to comply with the protocol. 4. Provide written informed consent before study participation.

SYNOPSIS

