7. ASSESSMENT OF HAND FUNCTION

Hand function will be assessed by the following:

1. QuickDASH questionnaire

The DASH outcome measurement is used around the world by clinicians and researchers as a tool for self-reported outcome concerning upper-limb musculoskeletal disorders (Hudak P). It consists of two components: symptom questions of 30 items with scores from 1 to 5, and optional high performance (sport/music or work) section of 4 items also with scores of 1 to 5.

The optional modules which concern sport, music or work are not used as those are mainly utilized to identify the specific limitations by professional athletes and performing artists or other group of workers.

This study will be using the abbreviated, QuickDASH questionnaire. The purpose of the QuickDASH is to use 11 items to measure physical function and symptoms. It decreases responder and data entry burden while maintaining a high degree of correlation to the original length DASH.

2. *Pinch grip by use of a pinch grip dynamometer*. Baseline® Mechanical Pinch Gauge (Baseline Medical, Quakertown, PA, USA) will be used to measure pinch force between thumb and forefinger. This device is CE certified and is commonly used by physiotherapists. It is utilized to evaluate tendon or nerve injury and neuromuscular disorders. Pinch strength will be recorded in kilograms.

3. Hand Grip Test (using a Jamar Hand Hydraulic dynamometer)

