14.2 Analysis of Secondary Outcomes

The composite outcome of hand function will be compared at 12-months post-operation using the average z-score approach outlined in the primary outcome analysis. The success rate, hematoma, bleeding, and radial artery occlusion will be compared between rDA and pDA cohorts using a Chi-square test (or Fisher's exact test). The rate of complications (including occurrence of hematoma, bleeding, radial artery occlusion, and complications of vascular access) per subject will be compared between the study cohorts using a Poisson Exact test.

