14.4 Sample Size

A Monte Carlo simulation study was utilized to study the sample size necessary to achieve at least 80% power to detect a small clinical difference between dRA and pRA in the primary composite outcome of hand function. A small clinical effect is defined as a $10\% \pm 10\%$ change in pre- to post-operation scores in at least one of the three tests for one of the study cohorts. Results from the Monte Carlo study indicate that a sample size of n=125 per group is sufficient to achieve at least 80% power under a correlation of 0.3 between the three tests. Allowing for a loss-to-follow-up rate of 15%, the total number of patients that should be enrolled for the entire study is at least 296 (148 per arm).

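### The primary composite averages QuickDASH, where higher is worse, with pinch and grip strength, where higher is better, and reverses no sign, so concordant harm cancels

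*Combined protocol and SAP*

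**What the plan says.** Section 14.1 builds the primary outcome for each subject as "the average of the z-scores of the differences between pre- and 1-month post-operation measurements for three individual tests" and compares it between arms with a Wilcoxon rank-sum test. The three components are:

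- **QuickDASH:** "the QuickDASH questionnaire score (0-100) calculated as [(sum of n responses / n) – 1] * 25". The Abbreviations list expands DASH as "Disabilities of the Arm, Shoulder, and Hand Questionnaire", and section 7 describes the parent instrument as "symptom questions of 30 items with scores from 1 to 5".
- **Pinch strength**, in kg.
- **Grip strength**, in kg.

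Section 14.2 carries the composite to 12 months, "using the average z-score approach outlined in the primary outcome analysis". Section 14.4 states that 125 per group is "sufficient to achieve at least 80% power under a correlation of 0.3 between the three tests".

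The documents do not reverse any component, say which direction of the composite is favourable, or say whether the difference is post minus pre or pre minus post. Sections 14.1 and 14.2 plan no separate between-arm test of each component.

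**The concern.** An average of z-scores measures one thing only if every component points the same way. Here one points towards disability and two towards strength. A patient whose hand worsens on all three tests gets one z-score of one sign and two of the other, and these partly offset.

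Section 4.1 gives the reason for the trial: the distal artery runs near the radial nerve, so hand function might suffer. Injury that brings both symptoms and weakness is a plausible form of that harm, and it is the pattern this composite suppresses. With no component-level comparison planned, nothing else in the analysis would reveal the cancellation.

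Direction is also unclear. Worsening on QuickDASH alone and worsening on grip alone move the composite in opposite directions, so a significant result could not be read as better or worse hand function without taking it apart.

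**Working it through.** **Inputs from the plan.** Three components, equal weights, Wilcoxon rank-sum test (14.1); 125 per group, correlation 0.3, at least 80% power, 15% loss to follow-up (14.4).

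**Assumptions, because the plan is silent.** Two-sided alpha 0.05; normally distributed change scores; effects in SD units of change; the 0.3 applies to scores pointed the same way (the alternative is shown below); Wilcoxon efficiency 0.955 relative to the t-test.

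**The plan's own figure.** 125 / (1 − 0.15) = 147.06, which rounds up to 148 per arm and 296 in total. This matches 14.4. The 125 cannot be uniquely reproduced, because the effect on the SD scale and alpha are not given.

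**SD of the composite.** The variance of the mean of three unit-variance scores is (3 + 2 × sum of the pairwise correlations) / 9.

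- Aligned: the correlations sum to 0.3 + 0.3 + 0.3 = 0.9, so SD = √4.8 / 3 = 0.730.
- As written: both correlations involving QuickDASH change sign, so the sum is 0.3 − 0.3 − 0.3 = −0.3 and SD = √2.4 / 3 = 0.516.

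**Equal worsening d on all three tests.**

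- Aligned: shift d, standardized effect d / 0.730 = 1.369d.
- As written: shift (d + d − d) / 3 = d/3, standardized effect (d/3) / 0.516 = 0.645d.
- Ratio of required sample sizes: (1.369 / 0.645)² ≈ 4.5.

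**Power at 125 per arm**, as Φ(δ√(125 × 0.955 / 2) − 1.96) plus the negligible opposite tail, with δ the standardized effect. For 0.3 SD on all three tests:

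- Aligned: δ = 0.411, δ√59.69 = 3.17, power 89%.
- As written: δ = 0.194, δ√59.69 = 1.50, power 32%.

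The number per arm for 80% power is 2 × (1.960 + 0.842)² / δ² / 0.955, which is about 98 aligned and about 439 as written.

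| Worsening (SD units) | Aligned | As written |
|---|---|---|
| 0.3 on all three | 89% | 32% |
| 0.26 on all three | 79% | 25% |
| 0.5 on all three | about 100% | 70% |
| 0.5 on QuickDASH and one strength test | 94% | 5% (shift exactly 0) |
| 0.5 QuickDASH, 0.25 pinch, 0.25 grip | 94% | 5% (shift exactly 0) |
| 0.8 on one test only | 80% | 98% |
| 0.3 on pinch and grip only | 56% | 85% |

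**Simulation check.** With 4,000 trials per scenario, z-scores taken on the pooled sample and the Wilcoxon test applied, power was 89% against 33% for 0.3 SD on all three tests, and 94% against 4.5% for 0.5 SD on QuickDASH and one strength test. For 1 SD on one test alone it was 91% against 99.6%. Type I error was about 5% either way.

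**If the 0.3 refers to raw, unreversed scores.** The two SDs swap. For 0.3 SD on all three tests, simulated power is 99% aligned and 18% as written, so the loss is larger.

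**The case against.** The strongest reply is that the plan is silent on alignment and does not forbid it. Section 14.1 names an established average z-score approach with two method citations, and the analysts may well intend to align the scores. The single positive correlation of 0.3 in 14.4 fits scores pointed the same way, which suggests the simulation may have aligned them already. It is also fair to say that:

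- the documents never state the direction of QuickDASH; it is inferred from the instrument's name and its symptom items;
- complete cancellation needs particular effect patterns, and with equal effects on all three tests one third of the shift survives;
- raw scoring has higher power when only one test moves or only the strength tests move, and the single-test case falls within the effect targeted in 14.4.

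These limits stand, and they bound the size of the problem. They do not remove it. Section 14.1 spells out the QuickDASH arithmetic and an explicit averaging rule but omits the step that decides what the average means. A citation does not write that step into the plan. If 14.4 did assume aligned scores, then the outcome that was powered differs from the one defined in 14.1. An unstated sign also leaves a choice about the primary endpoint that could be made after the data are seen.

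**Conclusion.** The primary composite is wrong as written, and the 12-month composite inherits the error. When symptoms and strength worsen together by equal amounts, two thirds of the shift is lost. At 0.3 SD on all three tests, power falls from about 89% to about 32%. When QuickDASH and one strength test worsen equally, power falls to about alpha. When only one test or only the strength tests change, no power is lost, but the sign of a single-test result depends on which test moved.

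The power figures rest on two-sided 0.05, normal change scores, correlation 0.3 on the aligned scale and effects in SD units, none of which the plan fully specifies. The offsetting itself depends only on higher QuickDASH meaning worse function. The figures of 125 per group and 296 in total are not shown to be wrong. This should be corrected before any unblinded analysis.

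**What to change.** Add to section 14.1: *Change is defined as post minus pre. The QuickDASH change z-score is multiplied by −1 before averaging, so that a higher value on each component and on the composite means better hand function.*

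State in section 14.2 that the same rule applies at 12 months. In section 14.4, confirm whether the Monte Carlo simulation used aligned scores and give the sign convention for the 0.3 correlation. If it used unaligned scores, rerun it with the corrected composite.

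The cost is one or two sentences of text and, at most, one rerun of the simulation. No extra data, visits or patients are needed.

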14.2 Analysis of Secondary Outcomes

The composite outcome of hand function will be compared at 12-months post-operation using the average z-score approach outlined in the primary outcome analysis. The success rate, hematoma, bleeding, and radial artery occlusion will be compared between rDA and pDA cohorts using a Chi-square test (or Fisher's exact test). The rate of complications (including occurrence of hematoma, bleeding, radial artery occlusion, and complications of vascular access) per subject will be compared between the study cohorts using a Poisson Exact test.

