5. STUDY OBJECTIVES

The primary objective of this study is to evaluate hand function following distal radial artery access compared to proximal artery access in patients undergoing cardiac catheterization.

Hand function will be assessed by:

- QuickDASH questionnaire
- Hand grip test
- Thumb forefinger pinch test utilizing a pinch gauge

Secondary endpoints include success rates, hematoma, bleeding, rates of radial artery occlusion and complications of vascular access.

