12.2. Potential Risks

12.2.1 Physical Risks

Possible risks include loss of sensory function in part of the hand if the cutaneous nerve running in the anatomical snuffbox becomes damaged, distal embolization can result in digital ischemia and occlusion of the branch supplying the scaphoid bone can result in bone necrosis.

A study with 656 patients reported an incidence of distal radial artery occlusion of 1.5%, haematoma of wrist and forearm (0,8%), edema (0.2%), numbress (0.6%), dissection (0.3%), arteriovenous fistula (0.2%), transient ischemic attack (0.2%), stroke (0.2%), aneurysm (0.2%), death (0.5%) (Kaledin AL, 2014;27).

A skilled and experienced operator minimizes such complications. Operators with adequate experience in distal radial access at the discretion of the Principal Investigator are eligible to participate.

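### The Poisson exact test of complications per subject pools four categories that are not defined as exclusive, so its error depends on unstated coding; one yes/no per subject is a cheap improvement

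*Combined protocol and SAP*

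**What the plan says.** Section 14.2 plans two kinds of safety comparison.

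- **Separate yes/no comparisons:** "The success rate, hematoma, bleeding, and radial artery occlusion will be compared between rDA and pDA cohorts using a Chi-square test", with Fisher's exact test as the alternative.
- **A pooled count:** "The rate of complications (including occurrence of hematoma, bleeding, radial artery occlusion, and complications of vascular access) per subject will be compared" between the arms "using a Poisson Exact test".

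The Synopsis lists the secondary objectives as "Vascular access success rates, hematoma, bleeding, complications of vascular access and radial artery occlusion". Section 5 has the same items: "Secondary endpoints include success rates, hematoma, bleeding, rates of radial artery occlusion and complications of vascular access". Section 12.2.3 names bleeding, hematoma and radial occlusion as the complications to be monitored up to one year. No section defines these terms, makes them mutually exclusive, or gives a counting rule. Section 14.2 names vascular-access complications only inside the pooled count. It plans no comparison of subjects with any complication against subjects with none.

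**The concern.** An exact Poisson comparison assumes independent events, so that the variance of each arm's total equals its mean. Even if each category is scored once per subject, two features break that assumption. A hematoma may also be recorded as bleeding, so one clinical event adds two counts. Two distinct events in the same subject have the same effect on the total.

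The fourth category adds to the uncertainty, because the text does not say whether it is a residual class or also covers the three named events.

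What is at stake is a safety p-value that changes with coding while the patients stay the same. With little overlap the test is conservative and loses power. With broad overlap it could suggest a difference that the yes/no comparisons beside it do not support.

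**Working it through.** **Inputs from the documents.** Section 14.4 gives 125 evaluable per arm and 15% loss to follow-up: 125 / 0.85 = 147.06, rounded up to 148 per arm, or 296 in total. This reproduces the stated figure. Section 12.2.1 quotes an earlier series with occlusion in 1.5% and haematoma in 0.8%, together 2.3%.

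**Assumptions.** The documents give none of these for this test: two-sided alpha 0.05; a proportion p of subjects affected, from 2.3% to 20%, equal in both arms under the null; a share q of affected subjects adding two counts, the rest adding one.

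**Direction of the effect.** For small p, variance/mean of the count is about (1 + 3q)/(1 + q). This is 1.00, 1.18, 1.40, 1.67 and 2.00 for q = 0, 10%, 25%, 50% and 100%. Against this works the discreteness of the exact test, which is conservative when counts are small.

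**Exact type I error.** The per-subject distribution (0, 1 or 2 counts) is convolved over 148 subjects per arm. The test rejects when 2 × P(Bin(T, 0.5) ≤ smaller total) ≤ 0.05, where T is the sum of the two totals. Probabilities are summed over all pairs of totals. Chi-square (uncorrected) and Fisher are applied to one yes/no per subject.

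| p | q=0 | 10% | 25% | 50% | 100% | Chi-square | Fisher |
|---|---|---|---|---|---|---|---|
| 2.3% | 1.4% | 2.6% | 4.5% | 7.5% | 12.5% | 4.5% | 1.4% |
| 5% | 2.4% | 3.8% | 5.9% | 8.6% | 11.4% | 4.8% | 2.4% |
| 10% | 2.3% | 3.8% | 6.0% | 8.9% | 11.9% | 5.0% | 3.3% |
| 15% | 2.3% | 3.8% | 5.9% | 8.4% | 11.5% | 5.2% | 3.4% |
| 20% | 2.0% | 3.4% | 5.3% | 7.8% | 10.7% | 5.0% | 3.6% |

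The Poisson error passes 5% only when about 20–30% of affected subjects add two counts.

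**At the Section 12.2.1 rates** (occlusion and haematoma assumed in different subjects, same rates in both arms): 3.5% if half of haematomas also count as bleeding, 5.7% if all do. At 125 per arm these are 3.0% and 5.0%.

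**Power at 148 per arm**, same q in both arms:

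| Affected | Chi-square | Fisher | Poisson q=0 | 10% | 25% |
|---|---|---|---|---|---|
| 15% vs 5% | 83.8% | 79.1% | 74.9% | 77.8% | 81.5% |
| 10% vs 2.3% | 82.0% | 74.4% | 73.6% | 76.6% | 80.2% |
| 20% vs 10% | 68.7% | 62.4% | 56.2% | 60.4% | 65.2% |
| 20% vs 8% | 86.2% | 82.1% | 77.7% | 80.2% | 83.3% |

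**Hypothetical example: 16 vs 8 affected subjects.** Chi-square = 296 × (16×140 − 8×132)² / (148 × 148 × 24 × 272) = 2.90, p = 0.088; Fisher p = 0.13. The Poisson p is 0.15 for totals 16 vs 8, 0.099 if a quarter count twice (20 vs 10), 0.065 if half do (24 vs 12), and 0.029 if all do (32 vs 16).

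**The case against.** A reader might infer that the planned test is anti-conservative. The documents do not support that. They give no overlap share, and the test is below or near nominal until about a fifth of affected subjects add two counts. Occlusion, the larger of the two quoted rates, is found by Doppler (Section 9.4) and is not naturally also a bleed.

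A reader might also take 12.5% as the expected error. That needs the vascular-access category to repeat every named event. The category is listed beside the other three, and Section 12.2.1 names events that could fill a residual class, such as dissection, arteriovenous fistula and aneurysm. Full repetition is the least natural reading, though the text does not exclude it.

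Three further objections have weight:

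- Hematoma, bleeding and occlusion already have their own yes/no tests, and the opening of Section 14 assigns safety comparisons to standard two-sample and categorical tests. This limits the harm but supplies no defined overall complication summary.
- In the 16 vs 8 example, part of the gap between Fisher and Poisson is Fisher's own conservatism. This is accepted: Chi-square, named first in Section 14.2, gives 0.088, and no p-value falls below 0.05 unless every event counts twice.
- A rate per subject is a legitimate quantity, and a count-once rule would cure duplicate counting. That is so, but the rule leaves genuine second events in one subject, and with one count per subject the Poisson test is conservative and less powerful than Chi-square.

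**Conclusion.** The point holds as a minor one. The pooled test has no fixed error rate, because the plan leaves the counting to an unstated coding choice. On the stated assumptions the error runs from 1.4–2.4% (one count each) through 4.5–6.0% (a quarter adding two) to 7.5–8.9% (half adding two). At the only event rates in the documents it is 3.5–5.7% under haematoma/bleeding overlap. Inflation is therefore possible, not demonstrated.

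The case for change rests on the alternative being better. On one yes/no per subject, Chi-square holds 4.5–5.2% and Fisher 1.4–3.6% regardless of overlap. Chi-square has more power than the Poisson count in all four scenarios for q up to 25%. The results depend on the assumed alpha, event rates and overlap. Only one secondary analysis is affected; the primary outcome and sample size are not.

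**What to change.** In Section 14.2, make the summary outcome any access-related complication, scored yes or no once per subject. Compare arms by the Chi-square test, or Fisher's exact test if expected counts are small (at 2.3% affected they are 148 × 0.023 = 3.4 per arm). Report the risk difference with a 95% CI. Keep the separate comparisons of hematoma, bleeding and occlusion as planned.

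If the count is kept as a descriptive addition, count each clinical event once and limit the vascular-access category to events other than the three named.

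The cost is a change of wording before the data are seen. It needs no new data and no test that Section 14.2 does not already name. The loss is information on several distinct events in one subject. Where expected counts call for Fisher, power is 1–6 points below the Poisson count if a quarter of affected subjects have two events, although the Poisson error is then 4.5–6.0%. If each affected subject has one event, Fisher is 1–6 points above it.
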